### **3 STUDY DESIGN SUMMARY**

This is a first-in-human, single-center, randomized, double-blind, placebo-controlled, two-part study in healthy adult males and females of non-childbearing potential. Because the safety profile of PK10571 in humans is unknown and this is the first clinical study to assess PK10571 in humans, a single-ascending dose escalation design will be used in Part A of the study. Part B will be a multiple-ascending dose escalation design, to be run only after review of safety and pharmacokinetic data from Part A.

In the single ascending dose study (Part A) at least 4 dose levels of PK10571 will be tested:

An optional fifth dose level of up to may be added, based on safety and pharmacokinetic data from the first 4 cohorts. Subjects will be randomized into one dose cohort and receive either PK10571 or placebo. Within each cohort, 6 subjects will receive active drug and 2 subjects will receive placebo.

In the multiple ascending dose study (Part B), up to three dose levels of PK10571 will be tested. The daily dose will be administered daily for 7 days with close clinical monitoring. The dose for the first cohort of Part B will be determined by review of the safety and pharmacokinetic data from Part A by the Safety Review Committee. The dose interval for the first cohort of Part B (i.e., once daily, twice daily, or up to three times daily) will be determined by review of the safety and pharmacokinetic data from Part A by the Safety Review committee. Subsequent doses and dosing intervals will be determined by review of the safety and pharmacokinetic data from the prior cohort.

For both Part A and Part B, for each cohort, randomization will occur in 2 blocks as follows: In the first block, 2 subjects (sentinel subjects) will be randomized 1:1 to receive PK10571 or placebo; in the second block, 6 subjects will be randomized 5 PK10571: 1 placebo. If PK10571 is well-tolerated in the sentinel subjects, the remainder of the cohort (n = 6) will be randomized. There will be a minimum of 48 hours between dosing of the 2 sentinel subjects and the remainder of the cohort.

The safety, tolerability, and pharmacokinetics of PK10571 will be evaluated in each sequential cohort prior to each dose cohort escalation, assessing the totality of all the safety data prior to initiating the next cohort.

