### 5.10 Safety Monitoring and Procedures

5.10.1 Vital Signs

A full set of vital signs (blood pressure, pulse rate, respiration rate, temperature, and pulse oximetry) will be measured at screening, at 0 hour (predose), and at the end-of-the study visit (Day 11 of Part A and Day 35 of Part B).

In Part A, blood pressure, pulse rate, and pulse oximetry will be measured at the following times:

• 10 minutes and 1, 2, 4, 8, 12, 16, 24, and 48 hours postdose

Note: The information in this section for Part B applies to QD dosing only. The timing of vital sign measurements for BID and TID dosing are provided in Appendix 4 and 5, respectively.

In Part B, blood pressure, pulse rate, and pulse oximetry will be measured at the following times:

- 10 minutes and 1, 2, 4, 8, 12, 16, and 24 hours after Dose 1
- 1, 2, and 4 hours after Doses 2-6
- 10 minutes and 1, 2, 4, 8, 12, 16, 24 hours after Dose 7
- Day 9 (prior to discharge)
- Day 10
- Day 14

At the screening visit, each subject will have blood pressure measured in both arms. If there is no significant difference (i.e., greater than 15 mmHg) between the systolic

Gossamer Bio, Inc.

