5.10.2 Pulmonary Function Tests (Spirometry)

Part A: Pulmonary function tests (FEV1 and FVC; best of 3 reproducible maneuvers) will be performed at screening, check-in, at 1, 8, and 24 hours after dose administration, and at the end of the study (Day 11).

Part B: In the case of QD dosing, pulmonary function tests (FEV1 and FVC; best of 3 reproducible maneuvers) will be performed at screening, check-in, at 1, 4, 8, and 23 hours after administration of the first and last morning doses (Day 1 and Day 7), 1 hour after dosing on Day 4, on Day 14, and at the end of the study (Day 35).

In the case of BID dosing, pulmonary function tests (FEV1 and FVC; best of 3 reproducible maneuvers) will be performed at screening, check-in, at 1, 4, 8, and 23 hours after administration of the first morning dose on Day 1 and Day 7, at least 1 hour after the first dose on Day 4, on Day 14, and at the end of the study (Day 35).

In the case of TID dosing, pulmonary function tests (FEV1 and FVC; best of 3 reproducible maneuvers) will be performed at screening, check-in, and at 1 hour after the first morning dose on Day 1, Day 4, and Day 7, at least 1 hour before second dose on Day 1 and Day 7, 23 hours after the first morning dose on Day 1 and Day 7, on Day 14 and at the end of the study (Day 35).

Repeat spirometry will be allowed at the Investigator's discretion.

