#### 5.10.4 Electrocardiograms

All subjects will have ECGs performed at screening. All ECGs will be performed after subject has been in supine position for at least 5 minutes.

In Part A ECGs will be performed at the following times: predose, 10 minutes postdose, 2, 4, 8, and 24 hours postdose, and at the end of the study.

In Part B, ECGs will be performed at the following times (relative to the first dose): predose, 10 minutes postdose, 2, 4, 8, and 24 hours postdose, Day 9 (prior to check-out), Day 14, and at the end of the study.

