| Concomitant
medication
review         | Х         |              |              |         |            |           |           |         |         |         |         |          |          |          |          |          |          |                |        |        |   | X  | X  | X      |
| Vital signs and pulse oximetry a | X         |              | X            |         |            | Х         |           | Х       | Х       | X       | Х       |          | Х        | Х        |          | Х        |          | Х              | Х      | Х      | Х | Х  | Х  | Х      |
| Physical
examination b        | X         |              | X            |         |            |           |           |         |         |         |         |          |          |          |          | X        |          | X b | X      |        | X |    | X  | Х      |
| 12-lead ECG c                    | X         |              | Х            |         |            |           | Х         |         | Х       | Х       | Х       |          |          |          |          | Х        |          |                |        | Х      |   |    | Х  | Х      |
| Chest X-ray                                 | Х         |              |              |         |            |           |           |         |         |         |         |          |          |          |          |          |          |                |        |        | Х |    |    | X
o |
| Pulmonary
function tests d    | Х         | Х            |              |         |            |           |           | Х       |         | X       | Х       |          |          |          |          | Х        |          |                | X
e | X
e |   |    | Х  | Х      |
| PPD f                            | X         |              |              |         |            |           |           |         |         |         |         |          |          |          |          |          |          |                |        |        |   |    |    |        |
| TSH   | X         |              |              |         |            |           |           |         |         |         |         |          |          |          |          |          |          |                |        |        |   |    |    | Х      |

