| Adverse event assessment n            |           |              | •            |         |            |           |           |         |         |         |         | - X      |          |          |          |          |          |         |   |   |   |    |    | → |

BUN = blood urea nitrogen; CR = creatinine; ECG = electrocardiogram; FSH = follicle-stimulating hormone; hr = hours; HIV = human immunodeficiency virus; INR = international normalized ratio; min = minutes; PK = pharmacokinetic; PPD = positive purified protein derivative skin test; PT = prothrombin time; PTT = partial thromboplastin time;  $T_{max}$  = time of maximum concentration; TSH = thyroid stimulating hormone

- a) A full set of vital signs (blood pressure, pulse rate, respiration rate, temperature, and pulse oximetry) will be measured at screening, at 0 hour (predose), and at the end-of-the study visit on Day 35. Blood pressure, pulse rate, and pulse oximetry will be measured 10 minutes after the first dose and at the following hours after the first dose: 1, 4, 8, 12, 16, 24, then daily on Days 3-9 (48, 72, 96, 120, 144, 168, 192, and 216 hours postdose) and at the outpatient visits on Day 10 and 14. At the screening visit, each subject will have blood pressure measured in both arms. If there is no significant difference (i.e., greater than 15 mmHg) between the systolic blood pressure in each arm at screening, then at other times the subject may have blood pressure measured in one arm.
- b) Physical examinations will be conducted for all subjects at screening, predose on Day 1, and on Days 2, 4, 7, 9, 14, and 35.

Gossamer Bio, Inc.

CONFIDENTIAL

31 Jul 2018

- c) All subjects will have ECGs performed at screening and at the following times (relative to the first dose): predose, 20 minutes postdose, 2, 4, 8, and 24 hours postdose, Day 9 (prior to check-out), Day 14, and at the end of the study.
- d) Pulmonary function tests (FEV1 and FVC; best of 3 reproducible maneuvers) to be performed using spirometry. Repeat spirometry will be allowed at the Investigator's discretion.
- e) To be performed at 1, 8, and 24 hours post Day 7 dose.
- f) PPD test to be read 48-72 hours after placement.
- g) Safety labs (chemistry, hematology, coagulation, and urinalysis) will be collected at the following time points: screening, check-in, Day 2, Day 4, Day 7, Day 9, Day 14, and Day 35 (end of study)

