a: A full set of vital signs (blood pressure, pulse rate, respiration rate, temperature, and pulse oximetry) will be measured at screening, predose on Day 1, and at the end-of-the study visit on Day 35. Blood pressure, pulse rate, and pulse oximetry will be measured on Day 1 and Day 7 (times relative to the first dose of the day) at 10 minutes and 1, 4, 8, 12, 16, and 24 hours postdose, daily (predose) on Days 3-6 and 7-9, and at the outpatient visits on Day 10 and 14. At the screening visit, each subject will have blood pressure measured in both arms. If

Gossamer Bio, Inc.

CONFIDENTIAL

31 Jul 2018

there is no significant difference (i.e., greater than 15 mmHg) between the systolic blood pressure in each arm at screening, then at other times the subject may have blood pressure measured in one arm.

- b: Physical examinations will be conducted for all subjects at screening, before the first dose on Day 1, and on Days 2, 4, 7, 9, 14, and 35.
- c: All subjects will have ECGs performed at screening and at the following times on Day 1 and Day 7 (times relative to the first dose of the day): predose, 20 minutes postdose, 2, 4, 8, and 24 hours postdose, Day 9 (prior to check-out), Day 14, and at the end of the study.
- d: Chest x-ray will be performed on Day 35 if clinically indicated as determined by the Investigator.
- e: Pulmonary function tests (FEV1 and FVC; best of 3 reproducible maneuvers) using spirometry will be performed at screening, check-in, at 1, 4, 8, and 23 hours after administration of the first and last morning doses (Day 1 and Day 7), at least 1 hour after the first dose on Day 4, on Day 14, and at the end of the study (Day 35). Repeat spirometry will be allowed at the Investigator's discretion.
- f: PPD test to be read 48-72 hours after placement.
- g: Safety labs (chemistry, hematology, coagulation, and urinalysis) will be collected at the following time points: screening, check-in, Day 2, Day 4, Day 7, Day 9, Day 14 and Day 35 (end of study)
- h: To be performed before the first dose of the day on Day 1 and 10 minutes after the first dose of the day (or Tmax, based on analysis from previous cohort) on Day 1 and Day 7.
- i: To be performed before the first dose of the day on Day 1 and 5 minutes after the first dose of the day (or Tmax, based on analysis from previous cohort) on Day 1 and Day 7.

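### For once-daily Part B dosing, Section 5.10.1 and Table 7 footnote a give conflicting vital-sign and oximetry times; at its printed hours the footnote lacks 22 of the 23 sets required after Doses 2-7, including the serial Day 7 profile

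*Protocol*

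**What the plan says.** Two places in the protocol set the times of blood pressure, pulse and oximetry for QD dosing in Part B.

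- **Section 5.10.1** limits its Part B times to QD and sends the other regimens to Appendices 4 and 5. It asks for eight sets after Dose 1 (10 min and 1, 2, 4, 8, 12, 16 and 24 h), then "1, 2, and 4 hours after Doses 2-6", then "10 minutes and 1, 2, 4, 8, 12, 16, 24 hours after Dose 7", then Day 9 before discharge, Day 10 and Day 14. It also asks for a full set at 0 hour, before dosing, without saying whether this means Day 1 only or every dosing day.
- **Table 7 footnote a** is the QD events schedule. It asks for 10 min and 1, 4, 8, 12, 16 and 24 h after the first dose, "then daily on Days 3-9 (48, 72, 96, 120, 144, 168, 192, and 216 hours postdose"), and Days 10 and 14. In the grid, the row "Vital signs and pulse oximetry" marks 2 h on Day 1, then has one mark for Days 3-6 together and one for each of Days 7, 8 and 9.

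The corresponding footnotes for twice-daily (Table 9) and three-times-daily (Table 11) dosing place readings on both Day 1 and Day 7 "at 10 minutes and 1, 4, 8, 12, 16, and 24 hours postdose, daily (predose) on Days 3-6 and 7-9". They too omit 2 h and give only predose readings on Days 3-6, but they keep a serial Day 7 profile.

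QD is not yet fixed. Section 3 leaves to the Safety Review Committee "The dose interval for the first cohort of Part B (i.e., once daily, twice daily, or up to three times daily"), and later cohorts are decided in turn.

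**The concern.** Both texts are current, both govern the same regimen, and neither is given precedence. The 31 July 2018 summary of changes revises other Table 7 footnotes but not footnote a, so nothing marks either schedule as superseded.

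Vital-sign change is among the safety endpoints in SAP Section 3.1. Protocol Section 3.3 lists vital signs among the data reviewed before each escalation, and oxygen desaturation with dyspnea is part of the first stopping rule in Section 3.5. A site that builds its worksheets from Table 7 alone would schedule no serial readings after the last dose and no 1, 2 and 4 h readings after the middle doses, in a first-in-human study of an inhaled drug. There would be no Day 7 profile to set beside Day 1.

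QD ECGs do not fill the gap. Section 5.10.4 states "In Part B, ECGs will be performed at the following times (relative to the first dose"), and lists none on Day 7.

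The tables are affected as well. SAP Section 6.2.9 tabulates scheduled values only, so discretionary readings would appear in listings but not in the summaries. The SAP needs one agreed set of scheduled times.

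**Working it through.** There is no planned figure to reproduce, so the check puts both schedules on one clock.

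**Inputs.** Seven daily doses (Section 3.2), with Dose k at 24 × (k − 1) h: 0, 24, 48, 72, 96, 120 and 144 h. Study day = h/24 + 1.

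**Step 1: sets that Section 5.10.1 requires.** After Dose 1: 8. After Doses 2-6: 5 × 3 = 15. After Dose 7: 8. Dose-timed total: 8 + 15 + 8 = 31, of which 15 + 8 = 23 follow Doses 2-7. Adding Days 9, 10 and 14 gives 34.

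**Step 2: sets in footnote a.** Seven after Dose 1, eight at 48, 72, 96, 120, 144, 168, 192 and 216 h, and Day 14: 7 + 8 + 1 = 16. Day 10 is counted once, because 216/24 + 1 = 10.

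**Step 3: match at the printed hours.**

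| Block | Required by 5.10.1 | In footnote a | Missing from footnote a |
|---|---|---|---|
| After Dose 1 | 8 | 7 | 1 (2 h) |
| After Doses 2-6 | 15 | 0 | 15 |
| After Dose 7 | 8 | 1 (168 h = 144 + 24) | 7 |
| Days 9, 10, 14 | 3 | 3 (192 h, 216 h, Day 14) | 0 |
| Total | 34 | 11 | 23 |

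After Doses 2-7 the footnote lacks 15 + 7 = 22 of 23.

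**Step 4: the reverse direction, same reading.** In footnote a but not explicitly in Section 5.10.1: 16 − 11 = 5, namely 48, 72, 96, 120 and 144 h, which are the times of Doses 3-7. These five are already covered if the 0-hour set in Section 5.10.1 means every dosing day.

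**Step 5: a lenient reading.** Ignore the hour labels and credit one post-dose set on each of Days 3-7 (5), plus 168 h (1). Then 23 − 6 = 17 are missing: 3 after Dose 2, 4 × 2 = 8 after Doses 3-6, and 8 − 2 = 6 after Dose 7. The five daily readings have been used as matches, so the reverse gap is zero.

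**Step 6: the footnote on its own terms.** Days 3-9 are seven days, but eight hour labels are printed. 192 h is Day 9; 216 h is Day 10, which the footnote lists again as an outpatient visit.

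**Step 7: per cohort of 8.** At the printed hours, 22 × 8 = 176 sets after Doses 2-7, of which 7 × 8 = 56 belong to Day 7 dosing. On the lenient reading, 17 × 8 = 136.

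**The case against.** The strongest reply is that the two lists do not exclude each other. Section 5.10.7 requires procedures to be completed as the protocol specifies, so a careful site would do both, and Section 5.10.1 allows additional vital signs. QD is one of three possible regimens. All of this stands, and it makes the loss conditional; it does not tell a site or a database builder which times are scheduled.

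It can also be said that 15 of the 22 missing sets follow Doses 2-6, where the twice-daily and three-times-daily footnotes are content with one predose reading a day on Days 3-6. That is fair. It is why the Day 7 series is the clearest unintended gap.

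The single marks in the Table 7 grid prove nothing either way. The pharmacokinetic row also has one mark on Day 7, although footnote j requires serial samples that day.

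Other monitoring remains: serial Day 7 spirometry, spirometry "1 hour after dosing on Day 4" (in Section 5.10.2, though the Table 7 spirometry row has no mark for Days 3-6), physical examinations on Days 2, 4, 7 and 9, a physician on site for at least 4 h after dosing, and adverse event monitoring.

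Two stronger readings are tempting, and the documents support neither:

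- A reader might infer that under footnote a nothing is measured for many hours after any of Doses 2-7. That assumes the readings at dosing times come before the dose. The footnote calls its 48-216 h readings postdose and does not place those at dosing times before or after that day's dose.
- A reader might combine a range of 17 to 22 missing sets with five missing in the other direction. The figures pair off: 22 with five, or 17 with none.

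**Conclusion.** Wrong as written. The QD vital-sign and oximetry schedule exists in two conflicting versions with no rule of precedence. Footnote a prints explicit hours, so the natural count is 22 of 23 sets missing after Doses 2-7 (15 of 15 after Doses 2-6, 7 of 8 after Dose 7). Five of its readings are then not explicitly in Section 5.10.1, subject to what the 0-hour set there means. Crediting the daily readings as post-dose sets gives 17 of 23 missing and no reverse gap. The omitted 2 h reading after Dose 1 and the surplus 216 h label hold on the printed text and suggest that the footnote, not Section 5.10.1, is the faulty text. The twice-daily and three-times-daily Day 7 profiles point the same way.

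The consequence rests on two conditions: QD is chosen, and footnote a alone is followed. The 176 sets per cohort are therefore an upper bound under those conditions, not an expected loss. Vital-sign data that are collected will be listed whichever text is used (SAP Section 6.12.3). The point should be corrected, but it does not call the design into question.

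**What to change.** Before any QD cohort is dosed, replace the times in Table 7 footnote a with those of Section 5.10.1:

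- 10 min and 1, 2, 4, 8, 12, 16 and 24 h after Dose 1;
- 1, 2 and 4 h after each of Doses 2-6;
- 10 min and 1, 2, 4, 8, 12, 16 and 24 h after Dose 7;
- Day 9 before discharge, Day 10 and Day 14.

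Delete the 216 h label. State in both places whether the 48-144 h readings are kept and, if so, label them predose on Days 3-7. Use this single list as the scheduled times for the vital-sign tables in SAP Section 6.12.3.

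The cost is a protocol clarification and matching database labels. The core change adds nothing to what Section 5.10.1 already requires (34 sets per subject between Dose 1 and Day 35). Keeping the five daily readings is optional: it brings the list to 34 + 5 = 39 sets per subject, or 5 × 8 = 40 more per cohort, all of them already named in footnote a.
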